# **Study Protocol**

# **Participant Flow**

#### **INTRODUCTION**

Lumbar disc herniation (LDH) is a localized displacement of the lumbar intervertebral disc into the vertebral canal or intervertebral space, and is considered as a mechanical disorder characterized by degeneration of the disc. 1-3 Disc herniation leads to functional loss and disability in daily life activities and negatively affects the quality of life among these patients. 4-6 Depending on LDH in sprawling of pain to spine and legs, lower extremity functions, especially walking, are adversely affected and usually walk slower than their healthy individuals. 7-9 The gait parameters are important gait variables, because they can be easily evaluated and measured to obtain gait deviations and walking difficulties, make a diagnosis, determine appropriate therapy, monitor the patient's progress, determine the prognosis, and they can help in understanding the functional limitations during gait.

#### **AIM**

The aim of this study was to emphasize on the interaction of spatial and temporal gait parameters and gait asymmetry in patients with Lumbar Disc Herniation (LDH).

#### **METHODS**

#### **Study Design**

This study is an observational, prospective, and cross-sectional study. This study recruited patients diagnosed with Lumbar Disc Herniation between May 2016 and December 2017 at Bahçeşehir University Goztepe Medical Park Hospital, Brain and Spine Surgery Department. Prior to conducting the investigation, ethical clearance was obtained from the ethics committee of the Bahçeşehir University Faculty of Medicine (22481095-020-482, 2016-04/07), and it was performed in terms of the guidelines of the Declaration of Helsinki.

#### **Inclusion criteria**

- (1) Individuals who were diagnosed with LDH by a specialist;
- (2) Patients had a medical history and proven by MRI with more or less evidence of degenerative lumbar disc;
- (3) Aged between 25-80 years old;
- (4) Pain symptom on lumbal area or lower extremity.

#### **Exclusion criteria**

- (1) Patients who have previously received a surgery or physical therapy treatment;
- (2) Having congenital deformity in the spine or lower extremity;
- (3) History of spinal surgery or other diseases affecting gait;
- (4) Pregnancy;
- (5) Situations that may cause gait balance problems;
- (6) Using assistive gait appliance.

### **Participants**

In total, 207 participants were included in this study as 153 patients with LDH (71 females, 82 males) and 54 healthy individuals in the control group (27 females, 27 males).

#### **Procedure**

In this study, the Analysis of the spatial and temporal gait assessment was performed using "Win-Track" gait analysis platform system (Medicapteurs, Balma, France). The dimensions of this device are 1610 mm × 652 mm × 30 mm (length/width/height); the thickness of the platform is 9 mm composed of 12288 resistive type sensors. The dimensions of these sensors are  $7.8 \times 7.8$  mm^2, and the acquisition frequency of the apparatus is up to 200 images/s enabling digitally recording the spatiotemporal information of subjects' gait based on the center of foot pressure. The participants were asked to continuously walk barefoot for ten times in their normal walking speed as straight as possible without any gait assist device on the "Win-Track" platform within the same day. The pain intensity of the patients was evaluated and recorded by a Visual Analog Scale (VAS) immediately before performing the analysis. Three flawless walking values analysis of spatiotemporal gait parameters were recorded and the arithmetic means were computed with three repetitions. Whenever they were about to take a rest, the patients were allowed to sit down on a chair. In addition, the analysis of spatiotemporal gait parameters and gait asymmetry of 59 participants who had the planned lumbar discectomy surgery, was tested before and 15 days after surgery. The analysis of the spatiotemporal gait parameters was performed on the healthy control group's participants by the same investigator using the same equipment and measurement protocol. The gait symmetry index was used to calculate the walking asymmetry.

**Main Outcome Measures** 

The demographic data of the participants were recorded on a personal information form on

the computer.

We used to Visual Analog Scale (VAS) for the Evaluation of Pain intensity.

The spatio-temporal data included the following values: step duration (seconds), gait cycle

duration (seconds), double stance duration (seconds), swing duration (seconds), step length

(cm), gait cycle length (cm), velocity (cm/s), and cadence (step/min); and these parameters

were separately recorded for right and left extremity.

The gait symmetry index (Symmetry Index= 2\*|X R-X L |/(X R+X L)\*100%) was used to

calculate the asymmetry between the left and right extremities during walking as a percentage.

Reporting of results

The results of this study will be presented at national and/or international meetings and will be

published in journals.

**Key Words:** Lumbar disc herniation, Gait analysis, Spatiotemporal gait parameters, Pain, Gait asymettry

**Funding:** No

References

1- Kreiner DS, Hwang SW, Easa JE, Resnick DK, et al. An evidence-based clinical guideline

for the diagnosis and treat- ment of lumbar disc herniation with radiculopathy. The Spine J.

2014;14(1):180-191.

2- Michael Luchtmann, Raimund Firsching. Lumbar disc herniation: Evidence-based

guidelines—a review. Indian Pract. 2016;69(3):36–41.

3- Fardon DF, Milette PC. Nomenclature and classification of lumbar disc pathology.

Recommendations of the Combined Task Forces of the North American Spine Society,

American Society of Spine Radiology, and American Society of Neuro- radiology. Spine

2001;26(5):93–113.

4- Chin KR, Tomlinson DT, et al. Success of lumbar microdiscectomy in patients with modic

changes and low-back pain: A prospective pilot study. J Spinal Disord Tech. 2008;21(2):139–

144

- 8- Teixeira da Cunha-Filho I, Lima FC, Guimarães FR, Leite HR. Use of physical performance tests in a group of Brazilian Portuguese-speaking individuals with low back pain. Physiother Theory Pract. 2010;26(1):49–55.

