Official Title: Preoperative and postoperative spatiotemporal gait parameters and gait asymmetry in patients with lumbar disc herniation: a prospective, cross-sectional study

Statistical Analysis Plan:

The Statistical Package for Social Sciences (SPSS) version 23.0, was used for the all statistical analysis (SPSS Inc., Chicago, IL, USA). Normality was analyzed using the Kolmogorov Smirnov test. The Independent t-tests for parametric, or Mann-Whitney U tests for non-parametric data, was used to compare the means between the two groups for demographic characteristics, and all the spatiotemporal gait parameters. Also, kruskal-wallis test, were applied to determine differences between LDH levels groups for pain intensity. The Paired t-test and Wilcoxon test were used to analyze the spatiotemporal gait values and gait symmetry in the patients with LDH before and 15 days after surgery and between healthy controls and 15 days after surgery. A p-value of <0.05 was considered to indicate a statistically significant difference.

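### As written, the unsigned symmetry index covers gait cycle duration and length, which have no true left-right difference, so a difference in gait variability could be reported as a difference in asymmetry

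*Protocol*

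**What the plan says.** Protocol, Main Outcome Measures, lists step duration and gait cycle duration, then "duration (seconds), double stance duration (seconds), swing duration (seconds), step length" and "cm), gait cycle length (cm), velocity (cm/s), and cadence (step/min); and these parameters", which it says "were separately recorded for right and left extremity". No parameter is exempted.

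The next paragraph gives the index as twice the absolute right-left difference over the right-left sum, in percent. Its purpose is to "calculate the asymmetry between the left and right extremities during walking as a percentage". X is not defined, and no subset of parameters is named there, in the Procedure section or in the SAP.

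On averaging, the Procedure section says: "Three flawless walking values analysis of spatiotemporal gait parameters were recorded and the arithmetic means were computed with three repetitions". It does not say whether the index is taken before or after averaging.

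The SAP states: "The Paired t-test and Wilcoxon test were used to analyze the spatiotemporal gait values and gait symmetry in the patients with LDH". The contrasts in that sentence are before v 15 days after surgery, and healthy controls v 15 days after surgery. Its separate sentence on independent two-group tests covers demographics and the spatiotemporal parameters and does not mention symmetry. Significance is p<0.05.

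**The concern.** A symmetry index is informative only where the two sides can truly differ. A gait cycle consists of one right step and one left step, whichever foot starts it. In steady straight walking the right and left cycles therefore have the same expected length and duration, however lopsided the steps are.

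Because the index is an absolute value, random error cannot average out to zero. On a shared parameter its expected value is proportional to within-person variability. Patients who walk less regularly than controls, or less regularly before surgery than after, would score higher with no change in symmetry. Gait asymmetry is in the study's stated aim and in the SAP title, so this bears on a main conclusion. The plan has no measure of within-person variability that would expose the problem.

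**Working it through.** The documents give no symmetry-index value, CV or power figure, so there is no stated result to reproduce.

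**Inputs from the documents.** "59 participants who had the planned lumbar discectomy surgery" (59, measured before and 15 days after); "153 patients with LDH (71 females, 82 males) and 54 healthy individuals in the control group" (54 controls); three walks averaged; alpha 0.05, taken as two-sided. **Assumed:** within-person CVs of 2% to 4%.

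**1. The index cannot see step asymmetry on a whole cycle.** Take illustrative steps of 60 and 54 cm.
- Step length: 2 × |60 − 54| / (60 + 54) × 100 = 10.5%.
- Cycle length: 60 + 54 = 114 cm on both sides, so the index is 0%.

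With step noise, successive overlapping cycles are (L1 + R1) and (R1 + L2). Their difference is L1 − L2, which is one leg compared with itself a stride later. With step CV c and three walks averaged, the SD of that difference relative to the cycle is c × √2 / 2 / √3 = 0.408c. The expected index is 100 × 0.408c × √(2/π).
- c = 2%: 0.65%.
- c = 4%: 1.3%.

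Simulation gives the same two values whether true step asymmetry is 0% or 10%. The index follows noise only.

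**2. Expected index when the recorded right and left values have independent errors.** With zero true asymmetry and CV c per side, E[index] ≈ 100 × c × √(2/3) × √(2/π):
- c = 2%: 1.30%
- c = 2.5%: 1.63%
- c = 3%: 1.95%
- c = 4%: 2.61%

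Correlation between sides would lower these means. It would not change the rejection rates below if the CV ratio is unchanged, because at zero asymmetry both tests depend essentially on the ratio.

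**3. Rejection rates with zero true asymmetry in everyone** (simulation, 3,000 to 4,000 replicates, index on three-walk means):

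| CVs compared | Ratio | 59 v 54: t / Mann-Whitney | Paired, n = 59: t / Wilcoxon |
|---|---|---|---|
| equal | 1.0 | about 5-6% / 5-6% | 4.5% / 4.5% |
| 2.5% v 2% | 1.25 | 33% / 25% | 33% / 29% |
| 3% v 2% | 1.5 | 79% / about 65% | 80% / 74% |

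Independent-sample tests were used for 59 v 54 because those are different people.

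**4. The noise effect by size of true asymmetry** (mean index at CV 2% v 4%):
- true asymmetry 0%: 1.31 v 2.61
- 1%: 1.54 v 2.72
- 3%: 3.04 v 3.64
- 6%: 6.00 v 6.09

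The inflation affects every parameter, but it is worst where true asymmetry is zero.

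**5. Order of averaging.** The one comparison run both ways was 153 v 54 at CV 2.5% v 2%. Rejection (t / Mann-Whitney) was 40% / 33% with the index on three-walk means, and 89% / 86% with the index taken per walk and then averaged.

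**The case against.** - **The plan never says outright that the index is computed on cycle duration or length.** True: this is the natural reading of a generic X that follows a list with no exclusions, not an explicit statement. If a subset was intended, it is not named, and the same amendment is needed.
- **A reader might infer that the index is pure noise on four of the eight parameters.** The documents do not support that, because they do not say how the device derives side-specific velocity and cadence. Derived per step, they can be truly asymmetric. Cadence then repeats the step-duration index, but velocity need not repeat anything. With steps of 60 and 54 cm and times of 0.60 and 0.54 s, the velocity index is 0% if the longer step takes longer (100 v 100 cm/s). It is 21% if the longer step is quicker (111.1 v 90 cm/s). The length and duration indices are 10.5% in both cases. Only cycle duration and length are securely affected.
- **A reader might attach the problem to all 153 patients v 54 controls.** Rejection there is higher (about 92% / 81% at a ratio of 1.5), but the SAP names symmetry only for the two contrasts that involve surgery.
- **A reader might count the redundant tests**, for example 24 gait tests falling to 16. That presumes separate right and left testing, which the SAP does not state.
- **Variability may not differ at all.** This stands. At equal CV the error rate is close to nominal, and nothing in the documents shows which case applies.

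**Conclusion.** The concern holds for gait cycle duration and gait cycle length. Following the text as it reads yields a symmetry result that cannot measure symmetry. It extends to velocity and cadence only if they are whole-cycle values, and to double stance only if it is total double support per cycle.

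The resulting error is conditional. For controls v post-surgery patients it ranges from about nominal at equal variability to 33% / 25% at a CV ratio of 1.25 and about 79% / 65% at 1.5. These figures rest on assumed CVs, zero true asymmetry and the index being taken on three-walk means. A reader might conclude that the study's asymmetry findings are artefacts; the documents do not support that, since they give no variability data for either group.

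**What to change.** 1. State in the SAP which parameters enter the index: step length, step duration and swing duration. Include double stance, velocity or cadence only if the device defines them per side or per step, and say which definition applies.
2. Report gait cycle duration, gait cycle length and any whole-cycle velocity or cadence once per person, without a symmetry index. Treat double stance likewise if it is a whole-cycle total.
3. Compute the index on the three-walk means.
4. Report the signed right-left difference or within-person variability across the three walks alongside the index, because the unsigned index is also noise-inflated on the retained parameters when true asymmetry is small. In simulation with zero true asymmetry (153 v 54, Welch test), the signed difference rejected in 5.8% of runs at CV 3% v 2% and 5.4% at 4% v 2%. It belongs beside the index, not in its place, because opposite-sided asymmetries cancel in a signed mean.

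The cost is SAP wording, one check of the device's definitions and a few fewer index values to report. The walks already recorded are sufficient.

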Official Title: Preoperative and postoperative spatiotemporal gait parameters and gait asymmetry in patients with lumbar disc herniation: a prospective, cross-sectional study

Statistical Analysis Plan:

The Statistical Package for Social Sciences (SPSS) version 23.0, was used for the all statistical analysis (SPSS Inc., Chicago, IL, USA). Normality was analyzed using the Kolmogorov Smirnov test. The Independent t-tests for parametric, or Mann-Whitney U tests for non-parametric data, was used to compare the means between the two groups for demographic characteristics, and all the spatiotemporal gait parameters. Also, kruskal-wallis test, were applied to determine differences between LDH levels groups for pain intensity. The Paired t-test and Wilcoxon test were used to analyze the spatiotemporal gait values and gait symmetry in the patients with LDH before and 15 days after surgery and between healthy controls and 15 days after surgery. A p-value of <0.05 was considered to indicate a statistically significant difference.

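### Both patient-versus-control gait contrasts are unadjusted, nothing follows if demographics differ, and the 15-day contrast with controls is listed under paired tests

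*SAP*

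**What the plan says.** The SAP is a single paragraph. For patients against controls it names an independent t-test or a Mann-Whitney test, which "was used to compare the means between the two groups for demographic characteristics, and all the spatiotemporal gait parameters". It mentions no covariate, regression, stratification or matching, and no consequence of a demographic difference.

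The next relevant sentence assigns the paired t-test and the Wilcoxon test to two comparisons: patients before and 15 days after surgery, and "between healthy controls and 15 days after surgery". The protocol (Procedure) gives the operated group as "59 participants who had the planned lumbar discectomy surgery". The Participants section gives 153 patients (71 female) and 54 controls (27 female).

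Controls were measured "by the same investigator using the same equipment and measurement protocol" (protocol, Procedure). That standardises the measurement, not who the controls are. The readable text gives no rule for selecting or matching controls, but nothing is legible under the Participant Flow heading, so the absence of such a rule cannot be asserted. It is also unclear which eligibility items bind controls. "Individuals who were diagnosed with LDH by a specialist" can only describe patients, while "Aged between 25-80 years old" names no group.

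**The concern.** These are non-randomised comparisons. Gait speed, step length and timing can vary with age and stature whatever the state of the disc, and the protocol records lengths and velocity in raw cm and cm/s with no stated scaling to body size. If the groups differ in age or height, an unadjusted contrast mixes that difference with the effect of LDH. The main weakness is an imbalance that the demographic test would show and the plan would then leave in place.

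Two gaps add to this. If "was used to compare the means between the two groups for demographic characteristics, and all the spatiotemporal gait parameters" refers to LDH patients against controls, no demographic comparison of the 59 operated patients with controls is described, although they have their own control contrast. And a paired test does not fit two sets of different people unless matched pairs exist.

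**Working it through.** **The plan's own figures.** The documents give no effect size, SD or power figure, so there is no design calculation to reproduce. The counts agree: 71 + 82 = 153, 27 + 27 = 54, 153 + 54 = 207. The proportion female is 71/153 = 46.4% against 27/54 = 50.0%. The sex split of the 59 is not given.

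**Assumptions, not in the documents.** No disease effect; true age difference d = 0.3 or 0.5 SD; within-group age-gait correlation r = 0.2 or 0.45; two-sided 5% test (the SAP does not state sidedness).

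**Unadjusted independent-groups test.** Bias = d × r in SD units. SE = sqrt(1/n1 + 1/n2), which is sqrt(1/153 + 1/54) = 0.158 and sqrt(1/59 + 1/54) = 0.188. The rejection rate is P(|Z + bias/SE| > 1.96).

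| d | r | Bias (SD) | p<0.05, 153 v 54 | p<0.05, 59 v 54 |
|---|---|---|---|---|
| 0.3 | 0.2 | 0.060 | 6.7% | 6.2% |
| 0.3 | 0.45 | 0.135 | 13.7% | 11.1% |
| 0.5 | 0.2 | 0.100 | 9.7% | 8.3% |
| 0.5 | 0.45 | 0.225 | 29.5% | 22.3% |

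**Split by the result of the age test.** Simulation with bivariate normal age and gait, 1,000,000 runs per scenario. Each pair of rates is for r = 0.2, then r = 0.45.

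| Contrast | d | Age test misses | Gait p<0.05 if missed | Gait p<0.05 if flagged |
|---|---|---|---|---|
| 153 v 54 | 0.3 | 52.9% | 5.33%, 6.49% | 8.16%, 21.58% |
| 153 v 54 | 0.5 | 11.8% | 5.56%, 7.94% | 10.17%, 32.18% |
| 59 v 54 | 0.3 | 64.9% | 5.21%, 6.04% | 7.84%, 20.09% |
| 59 v 54 | 0.5 | 25.0% | 5.57%, 7.61% | 9.15%, 26.80% |

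The two tables agree. For 153 v 54 at d = 0.3 and r = 0.45, 0.529 × 6.49% + 0.471 × 21.58% = 13.6%. The harm is concentrated in the samples where the age difference is visible. With age in the model the rate is 4.98% to 5.03% in all eight scenarios.

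**Precision after age adjustment.** SE ratio = sqrt((1 − r²) × (SE² + d²/(n − 2)))/SE, with n = 207 or 113.

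| d | r | 153 v 54 | 59 v 54 |
|---|---|---|---|
| 0.3 | 0.2 | 0.988 | 0.991 |
| 0.3 | 0.45 | 0.901 | 0.903 |
| 0.5 | 0.2 | 1.003 | 1.010 |
| 0.5 | 0.45 | 0.915 | 0.921 |

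**Paired listing.** One-to-one pairing of 59 with 54 leaves out at least 59 − 54 = 5 patients. With arbitrary pairing and no bias (100,000 runs), the false-positive rate is 5.1% for both the paired and the independent test. At a true 0.5 SD difference, power is 72% paired against 75% independent.

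**The case against.** The strongest reply is that no imbalance has been shown. Sex is the only demographic reported by group, and it is close. The size of the bias rests wholly on assumed inputs, and at the low end it is one or two percentage points above 5%. The return to 5% after adjustment is partly built in, because the simulation has one linear confounder and the model contains it. Adjustment cannot repair unknown control selection. Height is not named as a recorded variable and has no figure here. The precision figures are for age alone. All of this stands, and it makes the point conditional.

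The paired listing may be loose wording, and Wilcoxon could mean the rank-sum test. Arbitrary pairing would not inflate the false-positive rate. That limits the harm, but the sentence still names the paired t-test and no independent-samples t-test for this contrast. As written, the result would depend on an arbitrary row order.

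Matching or selection rules may sit in the illegible Participant Flow, and some eligibility items may apply to controls. The official title centres on before and after surgery, a comparison that is untouched. The SAP is in the past tense (SPSS "was used for the all statistical analysis"), so the data may already be analysed. That affects how an adjusted analysis is labelled, not whether it is useful.

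**Conclusion.** The concern holds and should be acted on, with medium confidence about its practical size. Three things can be read directly from the SAP: neither control contrast is adjusted, no action follows a demographic difference, and patients at 15 days against controls are placed under paired tests. The last needs no assumption about imbalance.

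The bias is conditional. Under the stated assumptions it is 0.06 to 0.225 SD, with false-positive rates that run from barely raised to about 30% (153 v 54) or 22% (59 v 54). Where the age test misses the difference, the rate stays at 5.2% to 7.9%. Where it flags the difference, the rate is about 8% to 32%. The documents do not show whether the real groups differ.

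**What to change.** - For both control contrasts, fit a linear model of each spatiotemporal gait parameter on group, age (continuous) and sex, plus height if recorded, with robust standard errors. BMI is not a substitute for height. Sex is included mainly because the split of the 59 is unknown. Fit the model whatever the demographic test shows.
- Report the adjusted mean difference with its 95% CI beside an unadjusted independent-groups test.
- Do not use a paired test for controls against patients at 15 days, for gait parameters or the symmetry index, unless matched pairs exist and are described. Adjusting the symmetry index is optional.
- Describe demographics for 59 v 54 as well as 153 v 54. State how controls were selected and which eligibility items applied to them.
- If the data were already analysed, label the adjusted model as added after the fact. If age was not recorded for controls, state that as a limitation.

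The cost is SAP wording and one model per parameter, using 2 to 3 further degrees of freedom out of 207 or 113 participants. For age adjustment under the assumptions above, the SE would be about 10% smaller to 0.3% larger (153 v 54) or 10% smaller to 1% larger (59 v 54). The effect of adding sex and height on the SE was not calculated.

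### As written, the SAP plans no pre-operative comparison of gait symmetry between LDH patients and controls, and gives its only patient-versus-control symmetry contrast a paired test

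*SAP*

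**What the plan says.** The SAP is one paragraph and names three sets of analyses.

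- **Independent groups.** t-tests or Mann-Whitney tests are used to "compare the means between the two groups for demographic characteristics, and all the spatiotemporal gait parameters". The two groups are taken here to be the LDH patients and the controls.
- **LDH levels.** A Kruskal-Wallis test is applied to pain intensity only.
- **Paired t-test and Wilcoxon test.** Their first stated purpose is "to analyze the spatiotemporal gait values and gait symmetry in the patients with LDH before and 15 days after surgery". The same sentence then assigns them a second contrast, this time with controls: "and between healthy controls and 15 days after surgery".

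The Protocol (Participants) reports "153 patients with LDH (71 females, 82 males) and 54 healthy individuals in the control group". Under Procedure, before-and-after testing is described for "spatiotemporal gait parameters and gait asymmetry of 59 participants who had the planned lumbar discectomy surgery", and a general sentence adds: "The gait symmetry index was used to calculate the walking asymmetry". Main Outcome Measures lists eight spatiotemporal variables, which "were separately recorded for right and left extremity". It then defines the symmetry index separately, as a formula to "calculate the asymmetry between the left and right extremities during walking as a percentage". The Aim refers to gait asymmetry in patients with LDH and does not restrict this to operated patients.

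**The concern.** A healthy control group measured with the same equipment lets the study say how far patients depart from normal. For symmetry, the plan as worded uses that group only after surgery. A before-and-after test in the 59 shows whether symmetry changed. It does not show whether patients were more asymmetric than healthy people to begin with, and it says nothing about patients without a post-operative measurement.

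The post-operative contrast with controls then carries all the patient-versus-control evidence on symmetry, and its stated method assumes pairs that do not exist. At stake is whether the study can make any sound statement about asymmetry in LDH relative to healthy people.

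**Working it through.** **1. Counts (Protocol, Participants and Procedure).** Patients: 71 + 82 = 153. Controls: 27 + 27 = 54. Total: 153 + 54 = 207, which agrees with the Protocol's figure.

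**2. Is symmetry inside the independent-groups sentence?** The wording can be compared across the documents:

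| Place | How symmetry appears |
|---|---|
| Protocol, Aim | named next to the spatial and temporal parameters |
| Protocol, Procedure (pre/post sentence) | named next to the spatiotemporal parameters |
| Protocol, Main Outcome Measures | defined separately, after the eight variables |
| SAP, official title | named next to the spatiotemporal parameters |
| SAP, independent-groups sentence | not named |
| SAP, paired/Wilcoxon sentence | named next to the spatiotemporal values |

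Wherever both are meant, both are named. On the documents' own usage, the independent-groups sentence leaves symmetry out.

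**3. Who enters a symmetry analysis?** Both parts of the paired/Wilcoxon sentence need a measurement 15 days after surgery, which is described for 59 patients. If those 59 are among the 153:

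- covered: 59/153 = 38.6%
- not covered: 153 − 59 = 94, and 94/153 = 61.4%

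**4. Do the planned contrasts supply the missing one?** For means in the 59, (pre − control) = (pre − post) + (post − control), so a point estimate could be pieced together. No test of it is planned, the identity does not hold for medians, and it does not reach the 94.

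**5. Can the post-operative contrast be paired?** It sets 59 patients against 54 different people, with no matching described. One-to-one pairing would leave out at least 59 − 54 = 5 patients. Which patients were paired with which controls would be arbitrary, so the result would depend on the order of the data file.

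**6. What the missing comparison could detect (illustration only).** The documents give no SD for the index and no power calculation. Assume equal SDs, two-sided 5% and 80% power. The detectable difference in SD units is (1.960 + 0.842) × √(1/n₁ + 1/n₂):

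- 153 vs 54: 2.802 × √(0.00654 + 0.01852) = 2.802 × 0.1583 = 0.44 (0.446 by the noncentral t)
- 59 vs 54: 2.802 × √(0.01695 + 0.01852) = 2.802 × 0.1883 = 0.53 (0.532 by the noncentral t)

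The index is an absolute difference over a sum, so it cannot be negative and is probably skewed. These figures are a rough guide, and the finding on coverage does not depend on them.

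**The case against.** The strongest reply is that this is loose wording. The SAP is a short summary in the past tense. The index is computed from the left and right spatiotemporal values, so the phrase about all the spatiotemporal parameters could be meant to include it. The general sentence in Procedure about using the index comes directly after the control measurements and is limited to no group. This stands as a possibility. A reader might infer that the sponsor left the analysis out or never did it, but the documents show only that it is not described.

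The Aim does not mention controls, and the official title centres on pre- and post-operative gait, for which a symmetry test is planned. This also stands. The need for the comparison is inferred from having a control group and from an aim about asymmetry in LDH; it is not a stated objective.

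Two further readings are tempting and go too far:

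- A reader might call the 94 non-operated. The Protocol does not give their surgical status. It only describes no before-and-after measurement for them.
- A reader might say that nothing planned covers the 94. That is true of symmetry only. As LDH patients they enter the spatiotemporal comparison, and nothing excludes them from the pain analysis.

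Nor is the lack of a CI peculiar to this gap, since the SAP plans no CI for any analysis.

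Finally, the Wilcoxon test might be read as the rank-sum test, which suits independent groups. But the SAP uses the Mann-Whitney name for that purpose, and the paired t-test would still be the parametric choice. The loose-wording reply therefore does not rescue the paired contrast.

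**Conclusion.** The point holds in two parts of different strength.

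- **Wrong as written:** the contrast of controls with patients 15 days after surgery is assigned a paired method for unrelated people, so its p-value would not be valid. This rests only on the absence of any described matching.
- **Missing as written, possibly through loose wording:** no planned test compares the symmetry index of LDH patients before surgery with that of the 54 controls, and 94 of 153 patients (61%) enter no planned symmetry analysis. This assumes that the 59 are a subset of the 153, which is the natural reading but is not stated.

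Taken together, the plan as worded contains no sound patient-versus-control comparison of gait symmetry at any time point. The before-and-after symmetry test in the 59 is properly paired and is unaffected. Had the comparison been specified, 153 versus 54 could detect about 0.45 SD under the assumptions stated in the check.

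**What to change.** 1. For post-operative patients versus controls, replace the paired method with an independent-groups test: a t-test, or Mann-Whitney if the index is skewed.
2. Add the symmetry index of the parameters recorded by side to the independent-groups comparison of all 153 LDH patients (for the 59, their pre-operative values) with the 54 controls. Give an estimate and 95% CI. Name the parameters. Report the 59 pre-operative patients versus controls as supportive.
3. If item 2 was intended from the start, say that the index was included. Label it post hoc only if it was not intended.

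**Cost.** A short SAP paragraph and no new measurements: values were recorded by side, and controls were measured by the same investigator with the same equipment and protocol. The downside is up to eight more tests in the main comparison, one for each listed parameter, and as many again if the supportive comparison is tested and not only estimated. The report should say how many were run and whether p-values were adjusted.
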